5. STATISTICAL ANALYSES

Details of the interim and primary statistical analysis to be conducted on data collected from Day 1 through Week 104 are detailed in Section 5.1 through Section 5.8. Details of the final analyses planned for the optional two-year extension of the study until Week 208 will be described in a subsequent version of this SAP or in a separate document.

5.1 GENERAL CONSIDERATION

In the following sections, for all continuous variables for which descriptive statistics are indicated, the following statistics will be reported: the number of observations, the mean, median, standard deviation, and minimum and maximum. The 25th and 75th percentiles (Q1 and Q3) will also be reported for selected tables. Descriptive summaries of discrete data will include frequencies expressed in terms of number and percentage of participants.

For safety endpoints, the baseline is defined as the last available assessment prior to first study drug intake. For all other assessments, the baseline is defined as the last available assessment before or on the day of first study drug intake, unless specified otherwise.

All PD analyses and all clinical efficacy analyses will be performed on the ITT analysis set, unless specified otherwise. Safety analyses will be performed on the SE analysis set, except for analyses of MRI findings which will be performed on the M-SE analysis set and analyses of home administrations by study partner that will be performed on the SE, OH-SE, or H-SE analysis sets, as appropriate.

All analyses will be purely descriptive or exploratory without any formal hypothesis testing. For exploratory tests, a two-sided significance level of 5% will be used.

In general, missing outcome data will not be replaced or imputed unless specified otherwise. Number and percentage of missing data points will be reported for each visit for key endpoints of interest.

In statistical models using change from baseline of a given outcome measure as the dependent variable, participants with missing baseline outcome measure will be

Gantenerumab—F. Hoffmann-La Roche Ltd

Statistical Analysis Plan: WN29722 (GRADUATION)

18

Clinical Study Report: gantenerumab - F. Hoffmann-La Roche Ltd

Protocol Number: WN29722

Report Number: 1117435

18

excluded from the analysis. There will be no imputation of baseline value for outcome measures.

The impact of the COVID-19 pandemic on the study and its conduct will be monitored and the overall impact will be assessed and described in the Clinical Study Report.

5.1.1 Visit Windowing

The analysis of data will be undertaken using reporting windows. As all the endpoints in the study are collected at different time frequencies, different sets of reporting windows will be applied depending on the frequency of assessments. In case of more than one assessment within a time window, the assessment with the date closest to the target (scheduled) day will be selected.

For amyloid PET assessments, time windows will be used ([Table 2](#)). Because of visit windowing, data collected at an early termination visit will be summarized at the appropriate time in the trial. For participants who have discontinued treatment early, if a PET scan is performed more than 56 days after the date of last dose, the PET scan will not be used for the analysis.

Table 2 Time Windows for Amyloid PET Endpoints

Visit	Target study day	Time window
Baseline	1	Up to day 1
Week 52	365	281, 449
Week 104	729	645, 813

For endpoints of home administration questionnaire (Caregiver or Patient), time windows will be applied ([Table 3](#)).

Table 3 Time Windows for Home Administration Questionnaire Endpoints

Visit	Target study day	Time window
Baseline	- (no baseline assessment planned)	- (no baseline assessment planned)
Week 36	253	2, 308
Week 52	365	309, 448
Week 76	533	449, 630
Week 104	729	631, 770

For cognitive and functional endpoints, time windows will be applied ([Table 4](#))

Table 4 Time Windows for Cognitive and Functional Endpoints

Visit	Target study day	Time window
Baseline	1	Up to Day 1
Week 24	169	2, 266
Week 52	365	267, 448
Week 76	533	449, 630
Week 104	729	631, 770

5.2 PARTICIPANT DISPOSITION

The analysis of participant disposition will be based on the ITT analysis set. The number of enrolled participants will be tabulated by geographical region, country, and site.

The number of participants enrolled, treated with study drug, discontinued study drug, discontinued study, and completed study will be tabulated. Reasons for study drug discontinuations and for study discontinuations will be listed and summarized.

Major protocol deviations, including major deviations with regard to the inclusion and exclusion criteria, will be summarized. Separate tables will be provided for COVID-19-related major protocol deviations and reasons for COVID-19-related major protocol deviations.

5.3 PRIMARY ENDPOINT ANALYSIS

5.3.1 Definition of Primary Endpoint

The primary endpoint for this study is the change from baseline to Week 104 in brain amyloid load, as assessed by amyloid PET imaging using florbetaben as ligand and quantified on the centiloid (CL) conversion scale. For the purposes of analysis, the screening amyloid PET scan may be considered the baseline evaluation.

Brain amyloid load will be quantified in terms of Standardized Uptake Value Ratio (SUVR), defined as the ratio of the tracer uptake in a target region of interest (ROI) to the tracer uptake in a reference ROI. The target ROI is a weighted composite of the following regions (left and right), where each region is weighted by its own volume: frontal, temporal, parietal lobes, anterior and posterior cingulate gyri. The reference ROI is the whole cerebellum. The whole cerebellum region is represented by a weighted average of Cerebellum Ventral, Cerebellum Dorsal (left and right), and Cerebellar White Matter.

For each participant at each visit, SUVR will be linearly transformed to the standardized CL scale using the following formula:

$$CL = 175.6 \times SUVR_{WC}^{FBB} - 174.2$$

The CL variable is the current common standard in the scientific community.

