6.4 PRIMARY AND SECONDARY ENDPOINT ANALYSES

6.4.1 Primary Endpoint

The primary endpoint for this study is the change from baseline to Week 104 in brain amyloid load, as assessed by amyloid PET imaging using florbetaben as ligand and quantified on the CL conversion scale, in participants exposed to a Q1W administration regimen of SC gantenerumab. For the purposes of analysis, the screening amyloid PET scan may be considered the baseline evaluation.

Details about the primary estimand definition and corresponding statistical model specification, including handling of missing data will be described in the Statistical Analysis Plan (SAP). For example, a linear mixed-effects model with change from baseline as dependent variable, and baseline value and visit as covariate may be used.

Descriptive summary statistics of the change from baseline to Week 104 in brain amyloid CL load will also be produced. Descriptive summaries of the primary endpoint will present the mean, standard deviation, median, and minimum and maximum.

To evaluate the impact of different amyloid PET radioligands on the quantification of the PD effect of gantenerumab, a supplementary analysis will be performed similarly to the primary endpoint on the sample of participants scanned with florbetaben or flutemetamol in this study (if applicable).

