3. SAMPLE SIZE DETERMINATION

Determination of sample size is relative to the sample of participants assessed by amyloid PET imaging using florbetaben. The sample size for this study is determined as the number of participants needed for the estimated change from baseline to Week 104 in amyloid PET load to fall into a 10 CL confidence interval (CI) around its true value. With a standard deviation of 25.67 CL (see below), 150 participants are required to fulfill this criterion. However, due to a lower than expected screen failure rate at the end of the enrollment period, a total of 192 participants have been enrolled.

The standard deviation of amyloid reduction was estimated using amyloid PET data from the ongoing Studies WN25203 (hereafter referred to as “SCarlet RoAD”) and WN28745 (hereafter referred to as “Marguerite RoAD”) open label extension (OLE) periods (based on a cutoff date of 14 October 2019), yielding a value of 25.67 CL.

Uncertainties of the parameters affecting the estimation (e.g., drop-out rate, study drug discontinuation rate, and standard deviation) were assumed to be equivalent to a decrease in sample size of up to around 35% and were corrected for accordingly. This drop-out rate is calculated based on Marguerite RoAD OLE at Week 104 that was ongoing at the time the study protocol was written. A sample size increase may be considered if factors external to the study would warrant a change to the sample size assumption.

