4. ANALYSIS SETS

The following analysis sets are defined:

Analysis Set	Definition
Intent to treat (ITT)	All enrolled participants (i.e., who gave informed consent, did not fail screening, and had at least one Amyloid PET scan with a valid quantitative measurement performed with either florbetaben or flutemetamol), whether or not the participant received the assigned treatment.
Safety-evaluable (SE)	All participants enrolled who received at least one dose of study treatment, whether prematurely withdrawn from the study or not.
MRI safety-evaluable (M-SE)	All participants of the SE analysis set who had at least one post-baseline MRI assessment.
Amyloid-PET-longitudinal	All participants in the ITT analysis set with a valid post-baseline quantitative amyloid PET measurement performed with either florbetaben or flutemetamol.
MRI modified intent-to-treat (MRI-mITT)	All participants in the ITT analysis set who had at least one valid volumetric MRI quantitative measurement.
MRI-longitudinal	All participants in the MRI-mITT with at least one valid post-baseline volumetric MRI quantitative measurement.

Opportunity for home dosing safety-evaluable (OH-SE)	All participants of the SE analysis set who did not discontinue study drug before week 26.
Home dosing by study partner safety-evaluable (H-SE)	All participants of the SE analysis set who received at least one dose of study treatment administered at home by caregiver / study partner.

ITT = intent to treat; H-SE = safety-evaluable with home dosing by study partner; M-SE = safety-evaluable with post-baseline MRI; MRI = magnetic resonance imaging; MRI-mITT = modified intent-to-treat with at least one valid vMRI measurement; OH-SE = safety evaluable with opportunity for home dosing by study partner; SE = safety-evaluable;.

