5.3.2 Definition of Primary Estimand

The scientific question of interest is to assess the effect of the intended study treatment on the PD endpoint, change from baseline to Week 104 in brain amyloid load, in participants treated with SC gantenerumab, in the absence of a substantial impact of the COVID-19 pandemic and as if treatment discontinuation would not have occurred.

In alignment with the Addendum to ICH E9, the primary Amyloid PET estimand is thus described by the following attributes:

- **Target Population:**
Early (prodromal to mild) AD population as identified by the inclusion and exclusion criteria, see the Protocol (version 3.0), Sections 4.1.1 and 4.1.2
- **Variable:**
Change from baseline to Week 104 in amyloid PET CL
- **Treatment:**
Prescribed study drug in a Q1W regimen, including up-titration to the target dose
- **Population-level summary:**
Variable mean in the ITT analysis set
- **Intercurrent events (ICEs):**
 - Substantial reduction in drug exposure due to the COVID-19 pandemic (defined as ≥ 4 missed dose-months)
 - Treatment discontinuation due to any reason

Considering that amyloid PET primarily aims at estimating the Pharmacodynamic effect of the drug, rather than a direct measure of clinical efficacy, reporting treatment effect estimated "as if there were no treatment discontinuations and no substantial reduction in exposure due to COVID-19 pandemic" (thus using a hypothetical strategy) addresses the scientific question of interest.

The ICE of substantial reduction in drug exposure due to the COVID-19 pandemic is defined as 4 or more dose-months (i.e., 16 weeks) of treatment missed due to COVID-19-related reason. One dose-month is defined as 4 weeks of dosing, i.e., one dose with a Q4W dosing frequency or two doses with a Q2W dosing frequency or four doses with a Q1W dosing frequency (at target dose). The threshold (4) on the number of missed dose-months was determined based on the following reasons:

- Based on the half-life of approximately 24 days of gantenerumab, plasma concentrations after 4 months' interruption at the target dose are expected to be below the concentration with the dose of 225 mg Q4W which was shown to be ineffective in SCarlet RoAD and Marguerite RoAD
- Comparability to the GRADUATE I and GRADUATE II studies which use the same cut-off.

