5.3.3 Main Analytical Approach for Primary Endpoint

Descriptive summary statistics for the brain amyloid CL load at baseline, Week 52 and Week 104 as well as the change from baseline to Week 52 and to Week 104 will be produced on both the ITT and Amyloid-PET-longitudinal analysis sets. Descriptive summaries of the primary endpoint will present the mean, standard deviation, median, and minimum and maximum.

A Mixed Model for Repeated Measures (MMRM) analysis will be used to estimate the mean change in CL from baseline to Week 52 and to Week 104 on the ITT analysis set. The model will include the change from baseline in CL as the dependent variable, while adjusting for visit (as categorical), apolipoprotein E allele $\epsilon 4$ (APOE $\epsilon 4$) status (as categorical; carrier vs non-carrier), baseline CL, and baseline CL-by-visit. Visit will be treated as the repeated variable within a participant. An unstructured variance-covariance matrix will be applied to model the within-participant errors; in the case of non-convergence, compound symmetry will be used, together with a robust estimator of standard error ("sandwich" estimator).

In line with the primary estimand definition, data acquired after the ICE "Substantial reduction in drug exposure due to the COVID-19 pandemic" (as defined above) or more than 56 days from date of last dose will be excluded from the analysis and treated as missing for the primary analysis purposes.

There will be no data imputation for missing data. However, the MMRM model provides unbiased estimates and valid inference in the presence of missing data, under the MAR (missing at random) assumption.

The least squares means at Week 52 and at Week 104 will be estimated and presented with a 95% CI.

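### Does the SAP leave it open which PET tracer feeds the primary amyloid result?

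*SAP*

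**What the plan says.** The primary endpoint is tied to one tracer. SAP 5.3.1 takes brain amyloid load "as assessed by amyloid PET imaging using florbetaben as ligand and quantified on the centiloid (CL) conversion scale" and prints a single linear conversion whose input is a florbetaben SUVR with the whole cerebellum as reference. Protocol 6.4.1 defines the endpoint in the same way. The sample size follows suit: "Determination of sample size is relative to the sample of participants assessed by amyloid PET imaging using florbetaben" (SAP 3).

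Other parts are worded more broadly:

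- The estimand variable in SAP 5.3.2 is "Change from baseline to Week 104 in amyloid PET CL", summarised as "Variable mean in the ITT analysis set". Neither names a tracer.
- SAP 4 admits to the ITT set an enrolled participant who "had at least one Amyloid PET scan with a valid quantitative measurement performed with either florbetaben or flutemetamol". It admits to the Amyloid-PET-longitudinal set an ITT participant "with a valid post-baseline quantitative amyloid PET measurement performed with either florbetaben or flutemetamol".
- Under SAP 5.3.3 the Centiloid summaries "will be produced on both the ITT and Amyloid-PET-longitudinal analysis sets", and the MMRM runs on ITT.

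Protocol 6.4.1 also promises that a "supplementary analysis will be performed similarly to the primary endpoint on the sample of participants scanned with florbetaben or flutemetamol in this study", on condition that this is applicable. SAP 5.3.4 to 5.3.5.1 list COVID-19 sensitivity analyses, the proportion at or below 24 CL, a completers analysis and home-dosing subgroups. They do not mention the tracer analysis.

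**The concern.** An estimand, its analysis sets and its endpoint ought to point to the same scans. Here the endpoint says florbetaben, the sets say either tracer, and the estimand says nothing. The data exclusions in SAP 5.3.3 cover the COVID-19 exposure event and scans more than 56 days after the last dose, but not tracer. A programmer working from the set definitions alone might put a flutemetamol SUVR through the florbetaben formula, or pair a flutemetamol baseline with a florbetaben follow-up. Either would put a measurement artefact into the one number the study is designed to estimate.

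The second worry is that a promised analysis has disappeared. The SAP states that its language takes precedence over the protocol, so a reader cannot tell whether the both-tracer analysis was dropped, was found not to apply, or still stands.

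**Working it through.** **Which scans give a primary value?** SAP 5.3.2 comes directly after the definition of the Centiloid variable and uses that term. SAP 5.3.5 refers back to the CL variable as the one defined for the primary analysis. The only definition available is the florbetaben formula in 5.3.1. The possible cases then resolve under rules already in the SAP:

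1. Florbetaben at screening and at Week 104: the change is computed with the printed formula.
2. Flutemetamol at screening: there is no florbetaben baseline. SAP 5.1 excludes participants without a baseline value from change-from-baseline models and does not impute baselines.
3. Florbetaben at screening, flutemetamol at Week 104: there is no primary value at that visit. SAP 5.3.3 does not impute. A florbetaben scan at Week 52 still contributes through the MMRM.

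**Why do the sets admit both tracers?** ITT serves more than the primary endpoint. SAP 5.1 uses it by default for all pharmacodynamic and clinical efficacy analyses, 5.2 for disposition and 5.5.4.2 for plasma biomarkers. A florbetaben-only ITT set would remove people from the cognitive and plasma results for no reason. The broad sets are also what the both-tracer analysis would need.

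**Can a reader see how many values lie behind a mean?** SAP 5.1 requires the number of observations for continuous summaries, and missing counts and percentages by visit for key endpoints.

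**What would a florbetaben-only analysis cost in precision?** Inputs are from SAP 3: SD 25.67 CL, a 10 CL interval, loss of up to around 35%, 192 enrolled. I read 10 CL as the full width and assume 95% confidence, which the SAP states only for the model estimates.

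- Evaluable number needed: (1.96 × 25.67 / 5)² = 101.3, so 102.
- The SAP's figure of 150: 102 / (1 − 0.32) = 150. At exactly 35% loss it would be 101.3 / 0.65 = 155.8, so 156. The stated 150 therefore corresponds to 32% loss, consistent with the SAP's approximate allowance.
- With 192 enrolled: 192 × 0.65 = 124.8 evaluable, and width 2 × 1.96 × 25.67 / √124.8 = 9.01 CL.
- If a share *f* used flutemetamol and gives no primary value, the width is 2 × 1.96 × 25.67 / √(124.8 × (1 − *f*)):

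| *f* (assumed) | 0% | 1% | 5% | 10% | 20% |
|---|---|---|---|---|---|
| Width (CL) | 9.01 | 9.05 | 9.24 | 9.49 | 10.07 |

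- The 10 CL target is met while 124.8 × (1 − *f*) ≥ 102, that is *f* ≤ 1 − 102/124.8 = 18.3%, or about 35 of the 192.

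The documents give no flutemetamol count, so *f* is an assumption throughout. Use of that tracer required exceptional circumstances and the sponsor's prior written approval.

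**The case for a change.** The strongest case is that none of this is spelled out. The formula is to be applied to every participant at every visit, the exclusion list does not name tracer, and the sponsor itself treats tracer as a source of variability: Protocol 3.3.6 chooses one ligand for that reason and describes the Centiloid scale only as less tracer-dependent. SAP 5.3.5 states no denominator for the 24 CL proportion. The SAP also cites a web source accessed on 28 July 2022, after the 30 June 2022 interim cut-off, so its authors could have known whether flutemetamol was in use.

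Part of this stands. The SAP does not say whether the both-tracer analysis applies, and it prints no flutemetamol conversion, which that analysis would need. One line in SAP 5.3.5 would tidy this, and naming florbetaben in the estimand variable would be a harmless clarification.

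The rest does not carry the point further. The formula's input is labelled as a florbetaben SUVR, so applying it to another tracer contradicts the formula itself. The 24 CL denominator is a question for all missing scans: if set size were used, dropout of around 35% would matter far more than a few flutemetamol participants. An access date for a reference does not show what scan data the authors had seen, and whether flutemetamol was used at all cannot be settled until the Week 104 scans are in. Finally, the SAP's precedence over the protocol concerns what the SAP says. It says nothing against a conditional analysis, and its either-tracer sets suggest the option was kept.

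**Conclusion.** No change to the plan is needed. Followed as written, it gives a florbetaben-only primary estimate, with participants lacking a florbetaben value handled by the existing baseline and missing-data rules. The gap is one of detail that an analyst fills sensibly: run the both-tracer analysis if flutemetamol scans exist, with the appropriate conversion, and otherwise record it as not applicable.

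The consequence is limited to traceability of a conditional, descriptive analysis in a study that tests no hypothesis. It is nil if no flutemetamol scan was acquired. Otherwise the cost to the primary result is a modest loss of precision, with the interval still within 10 CL up to about 18% flutemetamol use, given 35% loss, the SD of 25.67 CL and a 95% level. The conclusion rests on reading the estimand's Centiloid variable through SAP 5.3.1, which is the only definition the SAP offers.

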5.3.2 Definition of Primary Estimand

The scientific question of interest is to assess the effect of the intended study treatment on the PD endpoint, change from baseline to Week 104 in brain amyloid load, in participants treated with SC gantenerumab, in the absence of a substantial impact of the COVID-19 pandemic and as if treatment discontinuation would not have occurred.

In alignment with the Addendum to ICH E9, the primary Amyloid PET estimand is thus described by the following attributes:

- **Target Population:**
Early (prodromal to mild) AD population as identified by the inclusion and exclusion criteria, see the Protocol (version 3.0), Sections 4.1.1 and 4.1.2
- **Variable:**
Change from baseline to Week 104 in amyloid PET CL
- **Treatment:**
Prescribed study drug in a Q1W regimen, including up-titration to the target dose
- **Population-level summary:**
Variable mean in the ITT analysis set
- **Intercurrent events (ICEs):**
 - Substantial reduction in drug exposure due to the COVID-19 pandemic (defined as ≥ 4 missed dose-months)
 - Treatment discontinuation due to any reason

Considering that amyloid PET primarily aims at estimating the Pharmacodynamic effect of the drug, rather than a direct measure of clinical efficacy, reporting treatment effect estimated "as if there were no treatment discontinuations and no substantial reduction in exposure due to COVID-19 pandemic" (thus using a hypothetical strategy) addresses the scientific question of interest.

The ICE of substantial reduction in drug exposure due to the COVID-19 pandemic is defined as 4 or more dose-months (i.e., 16 weeks) of treatment missed due to COVID-19-related reason. One dose-month is defined as 4 weeks of dosing, i.e., one dose with a Q4W dosing frequency or two doses with a Q2W dosing frequency or four doses with a Q1W dosing frequency (at target dose). The threshold (4) on the number of missed dose-months was determined based on the following reasons:

- Based on the half-life of approximately 24 days of gantenerumab, plasma concentrations after 4 months' interruption at the target dose are expected to be below the concentration with the dose of 225 mg Q4W which was shown to be ineffective in SCarlet RoAD and Marguerite RoAD
- Comparability to the GRADUATE I and GRADUATE II studies which use the same cut-off.

